calculated for the primary endpoint of time to death or hospital re-admission within the 6 month post-discharge period, assuming an alpha level of 0.05, power of 0.80, and a ratio of treatment to placebo random assignment of 1:1. In sub-Saharan Africa, it is estimated that 2-15% of children aged less than 5 years died within 6 months of hospital discharge 15.5% of children who survived discharge from the district hospital re-admitted with the same diagnosis within 6-months[7, 9, 25] Assuming

an additional 5-10% of children are re-admitted for other conditions, we expect that re-hospitalizations will occur in 20.5 to 30.5% of children enrolled in the study. Combined with our expected fatality rate (2-15%), we expect the cumulative incidence of the combined endpoint to range from 22.5 to 45.5%. [25] Based on a previous trial of mass drug administration of a single dose of azithromycin in which a single dose of the antibiotic was associated with a 49% reduction in risk of death, we calculated sample sizes using estimates of reduction in risk ranging from 30-50% with the cumulative incidence range of 22.5 to 45.5%, and found the sample size required ranged from 90 to 550 children per treatment arm.[10] Using the most conservative estimates of a hazard ratio of 0.70 and 22.5% prevalence of re-admission/death, we need to enroll 1100 children in the study (550 per arm) to achieve adequate power. We will recruit an additional 300 children ($\approx 20\%$) to account for possible loss to follow-up, resulting in a total planned enrollment of 1400 children, or 700 per treatment group. When considering mortality alone, and estimated mortality ranges of 2-15%, we will have $>80\%$ power to detect hazard ratios ≤ 0.5 for mortality rates of $\geq 8\%$ and hazard ratios ≤ 0.6 for mortality rates $\geq 11\%$ (Figure 6). Although the ability to determine differences in mortality between arms will require either a high mortality rate or a large measure of effect, in Kenya, re-hospitalization is associated with as much as a 23.6-fold increased risk of death, indicating that this outcome is itself a severe outcome and an intermediate marker of death.[7]

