illness/morbidity, post-discharge medication use including antibiotic treatment, and current condition of the child (any hospitalizations, admission and discharge date of any hospitalization, alive or dead, date of death if applicable). If caregivers report a hospitalization, study staff will work with hospital staff to pull the hospital record of the re-admitted child and will abstract relevant information from the hospitalization, including use of antibiotics and other medications. In addition, study staff will work with hospital staff to monitor hospital admissions on a weekly basis to determine whether a previously enrolled child is re-admitted at the health facility and will follow-up on reported admissions. Study staff will capture and transcribe admission and discharge dates, date of death (if occurring in facility), diagnosis or causes of admission, medication administration, and length of stay from patient medical records. Caregivers will be encouraged, at enrollment and at each subsequent contact, to bring the child to the health facility where enrollment occurred for assessment and possible treatment of any medical conditions. If a child is admitted at a facility other than the designated study site, study staff will contact facility personnel at the relevant site to obtain information. If a caregiver or staff member reports that a child has died, study staff will review hospital records (if available) or conduct a standardized verbal autopsy at the household to ascertain the cause of death. The height, weight, and MUAC of the caregiver will be collected at the follow up visit as well.

Laboratory procedures and specimen collection and storage

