Aim 1. To compare rates of re-hospitalization and mortality in the 6 months following hospital discharge among Kenyan receiving 5-day azithromycin vs. placebo. Primary analyses will be intent-to-treat (ITT) based on randomization allocation to the 5-day course of azithromycin versus placebo. Cox proportional hazards regression analysis will be used to compare the rate of the mortality or first re-hospitalization, between the randomization groups. If the baseline assessment of randomization reveals an imbalance in characteristics between the treatment groups, we will evaluate these variables as potential confounders in a sub-analysis secondary to the ITT. Potential baseline confounders will be added stepwise in a multivariable model and maintained in the model if adjustment changes the hazard ratio by more than 10%. Mediating variables, such as post-discharge antibiotic use, will be considered in secondary analyses as time-varying covariates to elucidate possible mechanisms of effect. The rate of death or first re-hospitalization will be compared at 90-days and at 6 months post-randomization using Kaplan-Meier (K-M) survival analysis. In addition, we will conduct Cox regression and K-M survival analyses for time to mortality and time to re-hospitalization as separate endpoints to understand intervention effects on these outcomes individually.

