In order to ensure adequate power to detect a discernable clinically relevant difference between study groups in the primary outcome, we have combined hospital readmission with death. Preliminary studies suggest that sufficient numbers of children will reach this combined outcome. However, we have incorporated an interim analysis by the DSMB to review the accrued data and an adapted sample size could be considered if the combined event frequency is less than predicted. It is possible that since most children receive antibiotics during hospitalization, the benefit anticipated with the use of azithromycin based on previous trials of mass drug administration will not be observed. However, most hospitalized children are treated with penicillins, cephalosporins, gentamicin, or cotrimoxazole while in hospital and the broad spectrum of activity (including malaria prevention) and long half-life of azithromycin suggest that there may be additive treatment and/or prophylactic benefit. Interim analysis will allow us to determine whether children receiving specific agents during inpatient treatment are less likely to benefit and will allow us to adapt our study design, sample size, or approach if necessary. After discharge, it is difficult to ensure adherence with the full 5-day treatment course. We will attempt to improve adherence using the IMB model, as described, and will measure adherence using three different measures. In addition, the mortality benefit of azithromycin observed in Ethiopia was from a single dose and we will be able to directly observe the first dose.[10] While relying on caregiver report of mortality and morbidity may lead to bias due to outcome misclassification, this misclassification should not differ between randomization arms and therefore will be non-differential. Finally, resistance prevalence may be lower than predicted, limiting power to detect clinically relevant differences in resistance prevalence between the intervention arms. We will store all isolates in the event that a greater number of isolates are needed for antimicrobial resistance testing.

ETHICAL CONSIDERATIONS

Ethical approval

Study approvals will be obtained from the KEMRI SERU and the University of Washington IRB.

Risks to subjects

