Outcome	Azithromycin-treated group (N=)			Placebo-treated group (N=)			Effect Estimate		
	n	Person-time	Incidence rate (/100)	n	Person-time	Incidence rate (/100)	Hazard ratio	(95% CI)	p-value
Death or re-hospitalization									

In subgroup analyses, we will compare treatment effects in children whose caregivers report no additional antibiotic use over follow-up and separately, who report no additional azithromycin use specifically and in subsets of children defined by the following baseline characteristics: age, county of recruitment, HIV-exposure status, nutritional status, and discharge diagnosis. We will not conduct formal testing of interaction in these analyses. We will report within sub-group p-values but interpret as secondary sub-group analyses. Also in secondary analyses, we will allow more than one hospitalization and model the incidence of re-hospitalization by randomization arm using Anderson-Gill models.

We will report causes of death (and predisposing conditions in those deaths) by randomization arm (without statistical testing) as presented in Table 4.

Table 4. Causes of death by randomization arm

	Azithromycin-treated group (N=)	Placebo-treated group (N=)
Primary cause		
LRTI/Pneumonia		
Diarrhea		
Malaria		
Tuberculosis		
Other Infection		
Other non-infectious		
Predisposing conditions		
HIV		
Sickle cell disease		
Confirmed acquired condition		
Confirmed congenital condition		
None		

Statistical Analysis of Secondary Aims

In addition to the primary aim of the study to determine whether a short-course of azithromycin reduces risk of post-discharge morbidity and mortality, secondary aims include determining potential mechanisms and intermediate markers of an intervention effect, the impact of the antibiotic course on antimicrobial resistance in gut and nasopharyngeal pathogens, and correlates of post-discharge morbidity and mortality. The below tables outline these planned analyses.

Aim 2a. To evaluate possible mechanism(s) by which azithromycin may affect morbidity and mortality, by comparing reasons for re-hospitalization and prevalence of pathogens between the randomization arms.

Population	Dependent variable	Independent Variable	Covariates	Statistical model
------------	--------------------	----------------------	------------	-------------------

Reasons for re-hospitalization				

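### The SAP compares arms in two subsets chosen by antibiotic use after randomisation, and gives within-subgroup p-values for five baseline factors without any test of whether effects differ

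*SAP*

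**What the plan says.** SAP Section 6, Analysis Methods, announces: "In subgroup analyses, we will compare treatment effects in children whose caregivers report no additional antibiotic use over follow-up". It adds a second subset, with no additional azithromycin use, and subsets by five baseline factors: age, county, HIV exposure, nutritional status and discharge diagnosis. On inference it says: "We will not conduct formal testing of interaction in these analyses. We will report within sub-group p-values but interpret as secondary sub-group analyses".

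SAP Section 3 (Timing of Outcome Assessments) starts each child's clock at randomisation, so antibiotic use over follow-up is a later event. The protocol (Data Analysis, Aim 1) treats that use differently: "Mediating variables, such as post-discharge antibiotic use, will be considered in secondary analyses as time-varying covariates". SAP 5.0 does not carry that analysis over.

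The protocol (Follow-up Procedures) has two sources for antibiotic use. The follow-up questionnaire asks about "post-discharge medication use including antibiotic treatment, and current condition of the child". For a reported re-admission, staff "will abstract relevant information from the hospitalization, including use of antibiotics and other medications". The SAP does not say whether antibiotics given at the endpoint admission count as additional use.

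SAP Section 4 (Type I errors) calls secondary analyses hypothesis-generating.

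**The concern.** **Use-defined subsets.** Whether a child receives a further antibiotic can depend on the assigned arm and on how ill the child is. Restricting to non-users can therefore compare different kinds of children across arms, and a ratio other than 1.00 can appear with no treatment effect. The restriction also removes endpoint events.

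**Baseline factors.** These subsets keep the randomised comparison, but a p-value in each subgroup does not test whether the effect differs between subgroups. A reader who sees significance in one age band and not in the next will tend to infer effect modification, and the plan offers nothing to correct that. The protocol's Background expects antibiotics to help most in children with comorbid conditions, so differing effects by HIV or nutritional status are of real interest.

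**Working it through.** **1. The plan's own figure.** Protocol, Sample Size, Aim 1: HR 0.70, 22.5%, two-sided 0.05, power 0.80, 1100 children. Schoenfeld events = 4 × 2.8016² / (ln 0.70)² = 247, and 247 / 0.225 = 1098, which agrees. This takes 22.5% as the incidence over both arms. The SAP (Section 3, Sample size) makes it the placebo incidence, and I follow the SAP below.

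**2. Events.** Placebo risk 0.225, azithromycin risk 1 − 0.775^HR, with 560 per arm (after 20% loss) to 700 per arm. At HR 0.70 the azithromycin risk is 0.1634, giving 218–272 events. The protocol says "we calculated sample sizes using estimates of reduction in risk ranging from 30-50" per cent, so HR 0.50 and 0.60 are shown too.

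**3. Uniform effect, within-subgroup tests.** Power p = Φ(|ln HR| × √E / 2 − 1.96), with E the events in the subgroup. Exactly one of two halves significant: 2p(1 − p). Mixed result over four equal bands (SAP Table 2 has four age bands; equal sizes assumed): 1 − p⁴ − (1 − p)⁴.

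| True HR | Events | p per half | One of two significant | Mixed over four |
|---|---|---|---|---|
| 0.50 | 193–241 | 0.93–0.97 | 14–6% | 78–65% |
| 0.60 | 205–257 | 0.74–0.82 | 39–29% | 87% |
| 0.70 | 218–272 | 0.46–0.55 | about 50% | 70–77% |

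**4. Interaction power, HR 0.70 in one half and 1.00 in the other.** Events: 109–136 plus 126–157.5, total 235–293. SE = √(4/E₁ + 4/E₂) = 0.262–0.234. Power = Φ(0.3567/SE − 1.96) = 0.28–0.33. For 80% power, about (4 × 2.8016 / 0.3567)² = 987 events are needed.

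**5. Use-defined subset under a true null (assumed inputs).** Follow-up is scaled to 1. Each child has a gamma frailty u (mean 1, variance θ = 0, 1 or 2) acting on both events and antibiotic use. The event hazard is uL, with L set to give 22.5%. The outpatient antibiotic hazard is 0.5u in placebo, multiplied by m = 1.0, 0.7 or 0.5 under azithromycin.

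- *m = 1.0:* the ratio is 1.00 in every setting.
- *Use counted up to the event:* 0.88–1.05. At θ = 0, m = 0.5, L = 0.2549, placebo keeps 0.1789 events over 0.5484 person-time and azithromycin keeps 0.2001 over 0.6953. The ratio is 0.2878 / 0.3263 = 0.88. At θ = 2, m = 0.5 it is 1.05.
- *Use counted over all of follow-up:* 1.00–1.28. Mean frailty among non-users is 1/(1 + 0.5θ) in placebo and 1/(1 + 0.5mθ) under azithromycin. At θ = 2, m = 0.5 these are 0.50 and 0.67, a ratio of 1.33 at the start that falls to 1.28 over follow-up. At θ = 0 it is 1.00.
- *Endpoint-admission antibiotics counted, given to 80–95% (assumed):* the ranges become 0.87–1.06 and 1.00–1.30, a shift of at most about 0.02.

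**6. Events kept in the placebo arm, whole-follow-up counting.** At θ = 0 the share kept is e^(−0.5) = 0.61. At θ = 2, with L = 0.3325, it is [2^(−1/2) − (1 + 2 × 0.8325)^(−1/2)] / 0.225 = 0.42. That is 42–61% if admission antibiotics are not counted.

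If they are counted, the protocol expects that "we expect that re-hospitalizations will occur in 20.5 to 30.5% of children enrolled in the study". The low end gives 20.5/22.5 = 0.911 of endpoints as re-admissions. With deaths taken as unaffected, a further factor of 0.911 × (0.05 to 0.20) + 0.089 = 0.134–0.271 applies, leaving about 6–16%. On 126–157.5 placebo events, that is about 53–96 against 7–26. The 80–95% is my assumption. The protocol (Potential Challenges and Limitations) says only that "most hospitalized children are treated with penicillins, cephalosporins, gentamicin, or cotrimoxazole while in hospital".

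**The case against.** The strongest reply is that the SAP discloses all this. It says no interaction will be tested, labels the analyses secondary, and treats secondary results as hypothesis-generating. No stated aim concerns effect modification, and the interaction test has only 28–33% power. This lowers the weight. It does not restore randomisation or turn a set of within-subgroup p-values into a test of difference. Low power is a reason to report the interaction estimate with its interval, where the uncertainty is visible.

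It can also be said that the bias is hypothetical. That stands in part: it vanishes if azithromycin leaves later antibiotic use unchanged, and 1.30 is the extreme corner of the assumed range.

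Three stronger readings are tempting and not supported:

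- A reader might infer that the unstated rule on admission antibiotics sets the direction of the bias. It moves the ratio by about 0.02; the direction depends on the time window and on frailty. The rule matters for how many events remain. The SAP's reliance on caregiver report leans towards the questionnaire item, although a caregiver could mention inpatient drugs.
- A reader might apply 315 events (22.5% of 1400) at HR 0.70 and obtain higher power. That count puts the placebo rate in both arms, which does not fit HR 0.70.
- A reader might take the Background remark on comorbid conditions as a stated interest in effects by age or county. It does not reach that far.

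**Conclusion.** The point holds, with low to moderate weight. The two use-defined comparisons are not randomised comparisons, and the within-subgroup p-values cannot show whether effects differ by any of the five baseline factors.

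The baseline-factor figures rest on the design HR, the SAP's placebo incidence, up to 20% loss and equal subgroup sizes: about 50% disagreement between two halves, 70–77% mixed results over four bands, and 28–33% interaction power.

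The figures for the use-defined subsets (0.87–1.06 or 1.00–1.30 under a true null) are illustrations, because neither document gives antibiotic-use rates. They show that the result depends on a time window the SAP does not operationalise beyond the words over follow-up; they do not predict a bias of that size. Nothing here touches the primary mITT comparison.

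**What to change.** 1. **Use-defined subsets.** Drop both as treatment-effect subgroups, or relabel them as exploratory non-randomised comparisons and state the time window and whether endpoint-admission antibiotics count. Report post-discharge antibiotic use and azithromycin use by arm in all mITT children. If an antibiotic subgroup is wanted, SAP Table 2 already has two baseline items: antibiotics received in hospital and antibiotics prescribed at discharge. These answer a different question but keep the randomised comparison. If the protocol's time-varying analysis is wanted, add it to the SAP, label it non-randomised, and count only antibiotics started before the endpoint event.
2. **Baseline factors.** Add an arm-by-factor term to the site-adjusted Cox model for each of the five. For county, keep the site indicators and add only the arm-by-county term, because each site lies in one county. Use a joint test for factors with several levels, and one term per discharge diagnosis. Report interaction estimates with confidence intervals beside the subgroup hazard ratios and intervals. Base any statement that effects differ on the interaction, and keep the hypothesis-generating label.

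The cost is SAP wording and a few model terms on data already collected. Three limits remain. A null interaction will not show a uniform effect at this power. Antibiotic start dates recalled at 90 days and 6 months may be rough. The time-varying analysis stays open to confounding by illness.

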Aim 2a. To evaluate possible mechanism(s) by which azithromycin may affect morbidity and mortality, by comparing reasons for re-hospitalization, prevalence of pathogen carriage, and markers of enteric dysfunction between the randomization arms. To evaluate the association between azithromycin and rate of cause-specific re-hospitalizations (hospitalization due to diarrhea, acute respiratory infection, malnutrition, or malaria) we will use Anderson-Gill proportional hazards modeling with previous re-hospitalizations included as time-dependent covariates in the model to capture the dependent structure of recurrence times. Because we will not have granularity in the time points other than 90-days and 6-months for assessment of pathogen carriage, we will compare the prevalence of pathogen carriage at 90-days and 6 months by randomization arm using generalized estimating equations (GEE) with a Poisson link, exchangeable correlation structure, and will adjust for baseline presence of a bacterial pathogen. To determine whether an observed association between the intervention and pathogen carriage wanes over time, we will test the hypothesis that the prevalence ratios comparing carriage in intervention arms are the same at the two follow-up time points using a chi-squared test. For the random subgroup of children in the **Enteric Function Cohort**, we will create a composite disease activity score ranging from 0 to 10 as previously described.[63] We will model the mean composite intestinal inflammation score by treatment group using linear regression. If the baseline comparison of randomization arms reveals an imbalance in characteristics between the treatment groups, we will additionally adjust for these variables, including post-discharge antibiotic use, in the regression models. Additionally, we will compare baseline differences between children randomized into the **Enteric Function Cohort** to those who were not, in order to evaluate representativeness of the random sample.

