5. **Cause-specific deaths** will be determined by consensus among clinical investigators based on all available information (death certificate, medical records, physical exams performed as part of study procedures, and verbal autopsies). Verbal autopsies will also be performed using the Population Health Metrics Research Consortium Shortened Verbal Autopsy Questionnaire. Secondary to the cause-assignment by consensus, we will additionally determine cause using the SmartVA-Analyze tool applied to the Verbal Autopsy form which utilizes the Tariff 2.0 Method to assign cause.^[7] Causes assigned by the verbal autopsy tool will be reported secondary to the consensus-assigned cause because the information utilized for cause of death by consensus is likely to exceed that captured by the verbal autopsy questionnaire asked to the caregivers.
6. **Cause-specific re-hospitalizations** will be assessed by questionnaire (maternal recall of diagnosis) at day 90 and 180 follow-up visits and medical record review (discharge diagnosis).

In cases when both sources are available, information from the medical record will be prioritized. Because children can have more than one diagnosis, each diagnosis (diarrhea, pneumonia, malnutrition, or malaria) will be considered in separate analyses. Additionally, we will consider a combined diagnosis of diarrhea, pneumonia, malnutrition and/or malaria to capture the diagnoses we hypothesize to be more affected by azithromycin.

1. **Bacterial pathogen carriage** will be assessed based on microbiologic testing of stool/rectal swabs and nasopharyngeal swabs at 90 and 180-day follow-up visits. *Shigella*, *Salmonella*, and *Campylobacter* will be assessed in the stool and *Streptococcus pneumoniae* (*S. pneumoniae*) will be assessed in nasopharyngeal swabs.

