All enrolled children	Time to re-hospitalization (due to diarrhea, pneumonia, malaria, malnutrition)	Randomization arm (ITT primary and per-protocol secondary)	1) Site 2) adjusting for imbalanced baseline factors	Anderson-Gill
Enteric and nasopharyngeal pathogens				
All enrolled children	Prevalence of Shigella , Salmonella , Campylobacter , Cryptosporidium , Giardia @ 0, 3, & 6	Randomization arm (ITT primary and per-protocol secondary)	1) Site 2) adjusting for imbalanced baseline factors & baseline presence of pathogen	GEE with Poisson link & exchangeable correlation structure
	Streptococcus pneumoniae prevalence @ 0, 3, & 6	Randomization arm (ITT primary and per-protocol secondary)	1) Site 2) adjusting for imbalanced baseline factors & baseline presence of pathogen	GEE with Poisson link & exchangeable correlation structure

Aim 2b. To determine whether empiric administration of azithromycin at hospital discharge increases risk of antimicrobial resistance in commensal *E. coli* and pneumococcal isolates from treated children and their household contacts.

Population	Dependent variable	Independent Variable	Covariates	Statistical model
Resistance in enrolled children				
1. Random subset of enrolled children selected to be in the AMR sub-study 2. Children in AMR sub-study in whom E. coli was isolated	Prevalence of resistance to azithromycin and presence of extended spectrum beta-lactamase-producing E. coli . In secondary analyses, prevalence of ampicillin, chloramphenicol, ciprofloxacin, ceftriaxone, ceftazidime, gentamicin, trimethoprim-sulfamethoxazole @ 0, 3, & 6 months	Randomization arm (ITT primary and per-protocol secondary)	1) Site 2) Adjusting for imbalanced baseline factors & baseline presence of resistance 3) Adjusting for propensity score made up of factors predictive of likelihood that E. coli is isolated	GEE with Poisson link & exchangeable correlation structure. Wald tests to compare between arms and to test for time-interaction (waning in resistance from 3 to 6 months in AZM arm)
Resistance in household contacts				

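### The SAP tables for carriage and resistance list month 0 as a modelled outcome as well as a covariate; for carriage, fitting them as written pulls the arm effect toward 1

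*SAP*

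**What the plan says.** **SAP Section 6, Aim 2a table.** The dependent-variable cell for *S. pneumoniae* ends with "prevalence @ 0, 3, & 6"; the enteric-pathogen cell gives the same three visits. The only independent variable is randomization arm. The covariate cell lists two sets: first site, then "adjusting for imbalanced baseline factors & baseline presence of pathogen". The model is a Poisson GEE with exchangeable working correlation. No visit or arm-by-visit term appears in these rows.

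**SAP Section 6, Aim 2b table.** The *E. coli* and *S. pneumoniae* resistance cells, for children and for adult contacts, also end at three visits: "trimethoprim-sulfamethoxazole @ 0, 3, & 6 months". One covariate set reads "Adjusting for imbalanced baseline factors & baseline presence of resistance". These rows add Wald tests for the arm comparison and to "test for time-interaction (waning in resistance from 3 to 6 months in AZM arm").

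**SAP Section 6, Outcome Definitions.** Bacterial carriage "will be assessed based on microbiologic testing of stool/rectal swabs and nasopharyngeal swabs at 90 and 180-day follow-up visits". The resistance definition, by contrast, includes baseline isolates.

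**Protocol, Data Analysis, Aim 2a.** "we will compare the prevalence of pathogen carriage at 90-days and 6 months by randomization arm", with adjustment for baseline carriage and a test of whether the two follow-up prevalence ratios are equal. The Aim 2b text likewise compares resistance at 90 days and 6 months.

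**The concern.** The enrollment sample is labelled baseline, so randomization should make its true ratio between arms 1. If month 0 rows sit in the outcome vector and one arm coefficient spans all rows, that coefficient averages a visit with no effect into the two visits where an effect is possible. The same value then reappears as a covariate for itself in the second covariate set.

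Two analysts, one following the SAP tables and one following the protocol, would fit different models and report different ratios for the same data. Shrinkage would understate a benefit on carriage. If the resistance models were pooled in the same way, it would understate a harm.

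**Working it through.** **Inputs.** From the protocol's Sample Size section, Aim 2a: 56% *S. pneumoniae* carriage in placebo with a detectable ratio of 0.85 (or 1.15); 20% enteric bacterial carriage with a detectable ratio of 0.68 (or 1.36); power of at least 80% at each time point; two-sided alpha 0.05; 1:1 allocation. There are 700 children per arm; 20% loss leaves 700 × 0.8 = 560. The documents give no within-child correlation, so it is assumed and varied.

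**1. The plan's own figure.** Two-proportion test, pooled variance under the null, 560 per arm:
- 0.56 vs 0.476: power 80.4%; ratio 1.15: 82.0%.
- 0.20 vs 0.136: power 81.8%; ratio 1.36: 81.1%.

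The stated 80% per visit is reproduced.

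**2. One arm effect over months 0, 3 and 6.** With equal placebo prevalence and equal weight at each visit, and a ratio of 1 at month 0, the common ratio is (1 + 2·PR)/3.
- PR 0.85: (1 + 1.70)/3 = 0.900. Log effect kept: ln 0.900 / ln 0.85 = 0.648, so 35% is lost.
- PR 0.68: (1 + 1.36)/3 = 0.787. Log effect kept: ln 0.787 / ln 0.68 = 0.622, so 38% is lost.

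**3. Simulation check.** Poisson log-link GEE, exchangeable correlation, robust standard errors, main visit terms, 560 per arm, latent within-child correlation 0.1 and 0.4 (150 and 40 replicates). No site effect was simulated, so the model without the baseline covariate stands for the site-only set.

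| Model | Ratio, true 0.85 | Rejection rate | Ratio, true 0.68 | Rejection rate |
|---|---|---|---|---|
| Months 3, 6 + baseline | 0.85-0.86 | 0.98 | 0.66-0.68 | 0.96-1.00 |
| Months 0, 3, 6, no baseline covariate | 0.90 | 0.85-0.86 | 0.79 | 0.78-0.85 |
| Months 0, 3, 6 + baseline | 0.90-0.91 | 0.98 | 0.78 | 0.96-1.00 |

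The shrinkage is the same with and without the baseline covariate, so it comes from the month 0 outcome rows. With that covariate the rejection rate does not fall. With arm-by-visit terms the month 3 ratio returns to about 0.85-0.86 and 0.67-0.69, even with month 0 rows left in.

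**4. Like-for-like power without the baseline covariate.** The reference row above adjusts for baseline, so this step compares two unadjusted models. For 0.56 vs 0.476 the difference is 0.084 and the single-visit standard error is √[(0.56×0.44 + 0.476×0.524)/560] = 0.0298. Assume a correlation of 0.2 between visits on the observed scale.
- Two visits: SE = 0.0298 × √(1.2/2) = 0.0231; z = 3.64; power about 95%.
- Three visits: difference 2/3 × 0.084 = 0.056; SE = 0.0298 × √(1.4/3) = 0.0203; z = 2.75; power about 79%.

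The loss in the site-only model is therefore due to the month 0 rows.

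**5. Resistance, if pooled.** Take the SAP's hypothesised pattern (higher at 90 days, similar by 6 months) and assume a doubling at month 3 that is gone by month 6.
- Months 0, 3, 6: (1 + 2 + 1)/3 = 1.33.
- Months 3, 6: (2 + 1)/2 = 1.50.
- Month 3 alone: 2.0.

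Simulation with 200 per arm, an assumed 10% in placebo and correlation 0.3 (60 replicates) gave about 1.34, 1.52 and 2.02-2.03.

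**The case against.** The strongest reply is that the tables only outline the analyses and nowhere say that the arm effect is pooled over visits. The protocol speaks of a prevalence ratio at each follow-up visit, and the Aim 2b rows name a time-interaction, which cannot be tested with arm as the only term. The three visits may merely list when prevalence is measured, as SAP Table 1 does, and adjusting for baseline makes sense only if the follow-up visits are the outcomes.

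Much of this stands. Dilution requires a single arm term across all three visits, and visit-specific contrasts remove it. A reader might infer that every resistance model is biased and that a harm will be understated; the time-interaction test means the documents do not support that. A reader might also blame the baseline covariate, or expect lower power throughout. Step 3 shows neither: the adjustment is sound in itself, and power falls only without it.

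The benign reading does not settle the matter. The column is headed as the model's dependent variable, SAP Table 1 also lists enrollment under its outcome column, and the protocol's comparison of the two follow-up ratios has no counterpart in the SAP's carriage rows. For those rows a single arm effect is the natural reading.

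**Conclusion.** The SAP tables contradict the protocol on which visits are modelled and, for bacterial carriage, contradict the SAP's own outcome definition.

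**Carriage (Aim 2a).** Fitted as written, the arm ratio moves from 0.85 to about 0.90 and from 0.68 to about 0.79, a loss of 35-38% of the log effect. This assumes the same true ratio at both follow-up visits and equal prevalence and weight across visits. Simulated power in the site-only model is about 0.78-0.86, against 0.96-1.00 for months 3 and 6 with baseline adjustment, for assumed latent correlations of 0.1-0.4. With the baseline covariate the estimate shrinks but the rejection rate does not.

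**Resistance (Aim 2b).** The gap is one of specification: how month 0 enters the between-arm test is not stated. The figure of 1.33 in place of 2.0 applies only if the effect is pooled and the assumed pattern holds.

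That month 0 sampling precedes the first observed dose is inferred from the baseline label; the documents do not state the order. These are secondary aims, and the primary endpoint is unaffected.

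**What to change.** In the Aim 2a carriage rows and all Aim 2b rows of the SAP:
- set the dependent variable to months 3 and 6;
- keep month 0 only as a covariate and for descriptive reporting;
- include visit and arm-by-visit terms;
- report the prevalence ratio at each follow-up visit, as the protocol describes for carriage.

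Removing month 0 alone would not be enough for resistance, because an effect confined to month 3 would still be averaged with month 6 (1.50 in place of 2.0 in the example). SAP Table 1 should mark enrollment as a baseline measurement. The cost is SAP wording; no new data are needed.
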